12.1 Randomization Procedure and Blinding Consideration, Part A Only

At Visit 1, subjects enrolled in Part A of the trial will be randomized in a 1:1 ratio to receive vaccination with a single 100 μ g dose of ABNCoV2 or a 30 μ g adult dose of Comirnaty, stratified by age (<65 years versus \geq 65 years) and prior vaccination regimens.

Randomization strata in Cohort 1 include the following prior vaccination regimens, completed at least 3 months prior to trial vaccination: 1) 2 doses of mRNA vaccine (Comirnaty or Spikevax), 2) 1 dose or 2 doses of adenovirus-based vaccine (Vaxzevria or Janssen COVID-19 Vaccine), 3) 1 dose of adenovirus-based vaccine followed within 3 months by 1 dose of mRNA vaccine, and 4) other authorized primary vaccination regimen, if applicable.

Randomization strata in Cohort 2 include the following prior vaccination regimens, completed at least 3 months prior to trial vaccination: 1) 2 doses of mRNA primary vaccines plus 1 booster dose of mRNA vaccine (Comirnaty or Spikevax), 2) 1 dose or 2 doses of adenovirus-based primary vaccines (Vaxzevria or Janssen COVID-19 Vaccine) plus 1 booster dose of mRNA vaccine, and 3) other authorized primary vaccination and boost vaccination combinations.

Randomized assignments for subjects will be performed via an interactive voice or web response system (IVRS/IWRS) after confirmation of subject's eligibility as specified in Section 1.3.

To minimize the potential for bias, site personnel and subjects are blinded to vaccination assignment. Additionally, the BN and CRO study teams and statistical programming team will not have unblinded data until database lock/freeze for the primary analyses.

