12.6.2 Primary Analysis Methods

The neutralizing antibody titers to the SARS-CoV-2 index virus will be collected and quantified as described in Section 10. As all subjects are previously vaccinated, it is not expected that a large number of titer values will be below the limits of quantitation or detection. In the case a titer result is below the limit of detection, a value of half the limit of detection will be used for analysis purposes. In the event a titer value is at least the limit of detection but below the limit of quantitation, a value of half the limit of quantitation will be used for analysis purposes.

A generalized linear model will be used to compare the SARS-CoV-2 neutralizing antibody titers (on the log₁₀ scale) at 2 weeks after trial vaccination between the vaccination groups with age and baseline titers included as covariates. The least squares means and the corresponding 97.5% CI from the model will be back transformed to their original scale via exponentiation for ease of interpretation.

If the non-inferiority success criterion is met (lower bound of the 97.5% CI is \geq 0.67), the p-value from the same model will be reported to assess superiority.

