**Table 2: Details of Trial Design**

Design Element	Description
Study phase and study population	Phase 3, healthy adult subjects previously vaccinated for SARS-CoV-2
Design type	Part A: Parallel Part B: Single arm
Control Method	Part A: Active controlled, Comirnaty Part B: None
Blind level	Part A: Double blind Part B: Open label
Method of Assignment	Part A: Randomized 1:1 to a single dose of ABNCoV2 or Comirnaty, stratified by age group (<65 years vs. ≥65 years) and prior vaccination regimens, within each cohort. Part B: Non-randomized, all assigned to a single dose of ABNCoV2

Design Element	Description
Duration of Trial Participation	Screening: 2 Weeks Active Trial Phase: 4 Weeks Follow-up: 22 Weeks
Dose Adjustment Rules	Not applicable, single dose given on Day 1
Planned Interim Analyses	No interim analysis of immunogenicity is planned; however, a data monitoring committee will review cumulative safety data throughout the trial. No immunogenicity data will be reviewed prior to the primary analysis.
Timing of Primary Analysis	The primary analyses of immunogenicity and analyses of safety will be performed once all subjects within a trial part have completed the 8-week Follow-up 1 visit. Data will be cleaned through the 8-week timepoint. A data review meeting will be conducted to review the key trial data and determine if strategies to handle other intercurrent events are needed in addition to the strategies to handle the planned intercurrent events in a blinded manner. Treatment assignment will not be unblinded for the primary analyses until the data are locked and analysis populations and strategies to handle intercurrent events are set.
Timing of Subsequent Analyses	Follow-up analyses will be performed once all subjects have completed the 3 month and the 6 month follow-up visits, respectively. The final analysis for the trial will occur once all subjects have completed all follow-up or have withdrawn early from the trial and the database has been locked.

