### 2.1. Multiplicity Adjustment

The hypothesis test of non-inferiority of ABNCoV2 to Comirnaty in terms of neutralizing antibody titers for SARS-CoV-2 will be performed in Part A in up to 2 cohorts. A Bonferroni correction will be used to control the trial-wide type I error of  $\alpha = 0.025$ , one-sided. In the event a cohort does not meet the requirement of 400 evaluable subjects for the primary endpoint analysis, summaries for the under-enrolled cohort will be considered purely descriptive.

The key secondary endpoints, ratios of GMTs for the VOCs at 2 weeks after trial vaccination, will be formally tested in Part A for non-inferiority of ABNCoV2 to Comirnaty only in the cohort(s) in which the primary success criterion is met. If the primary success criterion is met in only one cohort, VOCs will be formally tested in that cohort only. A Bonferroni adjustment will be used such that each VOC non-inferiority hypothesis will be tested at the  $\alpha =$

$\frac{0.025}{\text{number of VOCs tested}}$  level. For example, if 3 VOCs are tested, each test will be performed at the

$\alpha = 0.0083$  level such that success would require the lower bound of a 98.3% CI to be at least 0.67. In the event that success criteria are met for both Cohort 1 and Cohort 2, the number of tests will multiply, and thus non-inferiority hypothesis will be tested at the  $\alpha =$

$\frac{0.0125}{\text{number of VOCs tested}}$  level so that the overall type I error rate will be no more than 5%.

Due to the challenges of finding non-boosted potential trial subjects during enrollment, Cohort 1 was under-enrolled for the primary analysis, even with extension of the enrollment period. Therefore, only Cohort 2 will be formally tested.

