In general, immunogenicity analyses will be performed using the IAS according to the vaccine to which the subject was assigned (ABNCoV2 or Comirnaty by randomization for Part A, ABNCoV2 for Part B). In Part A, subgroup analyses performed within randomization strata will be analyzed according to the randomization stratum the subject reported at the time of randomization, even if upon further review it is determined to be different than the actual grouping to which the subject should have been assigned. This is most likely the case for prior vaccination stratum in Part A. In case the difference between the derived randomization stratum and as-randomized stratum is different for >5% of subjects in Part A, an analysis will be performed using the stratum “as-derived” from the prior COVID-19 vaccination history data.

Because SARS-CoV-2 infection or receipt of an additional SARS-CoV-2 boost vaccine outside of the trial would affect immunogenicity results, kinetic analyses of immunogenicity at Week 13/Month 3 and Week 26/Month 6 will be based on a subset of subjects who have not been naturally infected or received additional boost vaccinations prior to the time point of interest. In addition, to ensure the same population is followed over time, only subjects who have results for

Week 13 or Week 26, respectively, will be included in these analyses. If the number of subjects eligible for the Kinetics Analysis Sets is more than the pre-specified sample size, subjects will be selected randomly.

All safety analyses will be performed on the Safety Analysis Set, and subjects will be summarized based on the vaccine actually received.

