### 4.2.2. Main Analytical Approach

The estimate of the primary estimand will be created using the IAS.

The geometric mean, 95 % CI, median, minimum, and maximum of SARS-CoV-2 neutralizing antibody results for Part A will be calculated within each cohort. Additionally, in Part A, the ratios of the GMTs between ABNCoV2 and Comirnaty will be provided along with p-values, 95% CI and 97.5% CI from a generalized linear model. Age and baseline neutralizing antibody results will be included as covariates in the model to compare between the vaccination arms. The Least Squares (LS) Means and CIs from the model will be back transformed to their original scale.

GMTs will be obtained by computing the arithmetic means and the corresponding 95% CIs on the  $\log_{10}$  scale, and then exponentiating the  $\log_{10}$  means and confidence limits to return the results to the original scale.

Figures of neutralizing antibody results with the GMT and fold increase for the index virus and each VOC will be plotted by cohort, and for both cohorts combined, for each vaccination arm in Part A.

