#### Part A Multiple Imputation Procedure

Assuming the post-vaccination  $\log_{10}$  neutralizing antibody results are normally distributed, MI will be used to create 100 complete data sets that will account for the random variability in the  $\log_{10}$  neutralizing results. MI sensitivity analyses will only be performed for the Part A cohort(s) formally tested for non-inferiority of ABNCoV2 to Comirnaty, and Cohort 1 and 2 analyses will be performed separately but using the same method. As enrollment in Cohort 1 did not meet the sample size requirement for the formal non-inferiority test, the MI procedure will not be performed for that cohort. Baseline  $\log_{10}$  neutralizing antibody results, Week 1  $\log_{10}$  neutralizing antibody results, race group, sex, age group (<65 years versus  $\geq 65$  years), and prior vaccination regimen will be used in the joint model to predict the  $\log_{10}$  neutralizing antibody value for the primary estimand time point at Week 2.

MI analyses will be performed in SAS using the PROC MI and PROC MIANALYZE procedures, employing a fully conditional specification (FCS) model. A minimum of  $\log_{10}$  of half of the LLOD will be set for imputed values to correspond to the observed data range. In addition, a seed of 19201 will be used for the procedure. Analyses will be performed separately for each cohort in Part A. Sample SAS code is provided in [Appendix 2](#).

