##### **4.3.1.2. Main Analytical Approach**

The VOCs for Part A will be analyzed using the same analysis methods as those for the primary estimand described above. The precision of the CIs will be adjusted based on the number VOCs included in the key secondary analyses. The decision regarding which VOCs to include will be finalized before sample analysis begins. The GMT ratios and CIs with coverage adjusted for the non-inferiority hypothesis testing will also be calculated.

If the non-inferiority success criterion is met for a VOC (lower bound of the adjusted CI is  $\geq 0.67$ ), the p-value from the same model will be reported to assess superiority.

Analyses of other VOCs may also be performed similarly but not subjected to formal testing; such comparisons thus will not affect the trial-wide type I error.

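### Part A is randomised by prior vaccination regimen, but the primary and VOC models leave regimen out without a reason; if regimen predicts Week 2 titer, the GMT-ratio interval is slightly too wide.

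*SAP*

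**What the plan says.** Protocol Section 12.1 stratifies Part A by age (<65 versus ≥65 years) and prior vaccination regimen. For Cohort 2, "Randomization strata in Cohort 2 include the following prior vaccination regimens", followed by three categories: mRNA primary plus mRNA booster, adenovirus-based primary plus mRNA booster, and other combinations. SAP Table 2 gives the same design: age group "and prior vaccination regimens, within each cohort".

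The analysis model is narrower. Protocol Section 12.6.2 compares log10 titers "between the vaccination groups with age and baseline titers included as covariates". SAP Section 4.2.2 agrees: "Age and baseline neutralizing antibody results will be included as covariates in the model to compare between the vaccination arms". Regimen appears in neither. For the key secondary endpoints, SAP Section 4.3.1.2 states: "The VOCs for Part A will be analyzed using the same analysis methods as those for the primary estimand described above".

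Regimen is used elsewhere. It is a subgroup factor (Protocol 12.6.4, SAP 4.2.5). It is also a predictor in the multiple-imputation sensitivity analysis, where "prior vaccination regimen will be used in the joint model to predict the" Week 2 value. Neither document says why it is absent from the main model, and no planned sensitivity analysis adds it.

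SAP Section 2.1 records that Cohort 1 was under-enrolled: "Therefore, only Cohort 2 will be formally tested".

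**The concern.** Stratifying by regimen balances it between the arms, which reduces the true variance of the treatment difference to the extent that regimen predicts the outcome. A model without regimen leaves that predictable variation in its residual. The reported standard error is then larger than the true one, and the interval is wider than the design warrants.

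The lower confidence bound in Cohort 2 decides the one formal primary test and opens the VOC tests, which use the same model. At stake is a little precision and power. The error runs in the conservative direction, so it cannot produce a false claim of non-inferiority, and it does not bias the ratio.

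**Working it through.** **Inputs from the documents** (Protocol 12.2.1, SAP 5.1): SD 0.52 on log10; margin 0.67; one-sided 0.0125 (97.5% two-sided interval); 1:1 allocation; 450 evaluable planned, 400 minimum; stated power about 90% and 86%.

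**Assumptions:** true GMT ratio 1 (not stated); normal approximation; r, the share of residual log10 variance explained by regimen after age and baseline titer, taken as 2%, 5% and 10%. The documents give no value of r.

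**Step 1: reproduce the stated power.** d = -log10(0.67) = 0.1739; z = 2.2414; SE = 0.52 × sqrt(4/n); power = Φ(d/SE - z).

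- n = 450: SE = 0.0490, power 0.9043 (stated 90%).
- n = 400: SE = 0.0520, power 0.8651 (stated 86%).

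Both reproduce with no covariate in the model.

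**Step 2: omit or include regimen.** Let SEm = 0.52 × sqrt(4/n) be the SE that the model without regimen reports, and SEt = SEm × sqrt(1 - r) the true SE under stratified randomisation.

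- Power, regimen omitted: Φ((d - z × SEm)/SEt)
- Power, regimen included: Φ(d/SEt - z)
- One-sided type I error, regimen omitted: 1 - Φ(z/sqrt(1 - r))
- Smallest observed ratio that passes: 0.67 × 10^(z × SE), with SEm if omitted and SEt if included

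| Assumed r | CI narrower with term | Power at 450, omitted → included | Power at 400, omitted → included | Type I error if omitted | Ratio needed at 450 with term |
|---|---|---|---|---|---|
| 2% | 1.0% | 0.9065 → 0.9102 | 0.8675 → 0.8723 | 0.0118 | 0.861 |
| 5% | 2.5% | 0.9099 → 0.9190 | 0.8712 → 0.8830 | 0.0107 | 0.857 |
| 10% | 5.1% | 0.9157 → 0.9329 | 0.8776 → 0.9005 | 0.0091 | 0.852 |

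Without the term, the ratio needed at 450 is 0.863 for every r. Even with regimen omitted, power exceeds the stated figures.

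**Step 3: allow for the covariates already planned.** Step 2 gives age and baseline titer no explanatory value. If they explain an assumed 20% of the variance, replace 0.52 by 0.52 × sqrt(0.8). Over r = 2% to 10%, the gain is then 0.2 to 0.8 points at 450 and 0.3 to 1.3 points at 400. The ratio needed at 450 without regimen becomes 0.67 × 10^(2.2414 × 0.52 × sqrt(0.8) × sqrt(4/450)) = 0.840.

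**Step 4: the case r = 0.** Regimen then explains nothing. Three levels cost 2 degrees of freedom, and power changes by less than 0.0001.

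**Step 5: simulation check at r = 10%.** Assumed: permuted blocks of 4 within 2 age × 3 regimen strata, regimen shares 60/25/15%, and 25% aged 65 or over. Power omitted → included was 0.909 → 0.931 at 450 and 0.873 → 0.899 at 400. Type I error was 0.0087 omitted and 0.0122 included. A separate simulation with regimen shares 70/20/10% at n = 450 gave ratios of CI width (omitted to included) of 1.000, 1.026 and 1.054 for r = 0, 5% and 10%. The formula gives 1/sqrt(1 - r) = 1.000, 1.026 and 1.054.

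**The case against.** The strongest reply is that nothing here is an error. Protocol and SAP pre-specify the same covariates, type I error is protected, and the planned power is reached without regimen. The size of the effect rests on an assumed r. A place in the imputation model does not show that regimen matters after age and baseline titer, since the same list holds sex and race group. Baseline titer may carry most of any regimen effect. Regimen may also be misrecorded: SAP Section 3 names prior vaccination as the stratum most likely to differ on review, and misclassification would shrink the gain. Finally, silence in SAP Section 4.8 means little, because that section lists changes from the protocol and keeping its covariates is not a change.

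Much of this stands, and it limits the size of the point. The smaller gains in Step 3 are the better guide if baseline titer is strongly prognostic, and r could be zero. The Section 4.8 remark carries no weight.

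It does not remove the point. The trial randomises by regimen, neither document says why the model ignores it, and the planned subgroup analyses do not adjust the overall interval. Including the term costs almost nothing if regimen is irrelevant and gains precision if it is not.

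**Conclusion.** The concern holds as a modest precision point. The primary and VOC models omit a factor that Part A randomises by, and no reason is given. If regimen predicts Week 2 titer beyond age and baseline titer, the interval is somewhat too wide and the test conservative. Validity, the ratio estimate and the stated power are not threatened.

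The size cannot be determined from the documents. Over the assumed r of 2% to 10%, the power gain is about 0.4 to 1.7 points at 450 evaluable and 0.5 to 2.3 at 400, or about half that if age and baseline explain 20% of the variance. These figures also assume a true ratio of 1 and apply to the index-virus test at one-sided 0.0125. No separate figure was computed for the VOC tests, whose alpha depends on how many are tested. The formal consequence falls on Cohort 2; in Cohort 1 only descriptive intervals are affected.

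**What to change.** Before unblinding, amend SAP Sections 4.2.2 and 4.3.1.2 and Protocol Section 12.6.2 to add prior vaccination regimen as a fixed effect (three levels in Cohort 2), alongside age and log10 baseline titer. Use the regimen as randomised. SAP Section 3 already analyses stratum subgroups "according to the randomization stratum the subject reported at the time of randomization". Where its rule of more than 5% mismatch is triggered, repeat the model with the derived regimen as a sensitivity analysis. State at the same time whether age enters as a continuous variable or as the <65/≥65 stratum, since neither document says.

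Any combined Cohort 1+2 model should carry a cohort term for the same reason, because randomisation is done within cohort.

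If unblinding has already occurred, keep the pre-specified model as primary and report the regimen-adjusted model as a labelled sensitivity analysis.

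The cost is one model term in text and code and 2 degrees of freedom in Cohort 2. The data are already collected.

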### 4.2.3. Sensitivity Analyses

All results excluded from the primary estimand analysis will be included with the sensitivity analysis for a full account of the trial population, i.e., the safety analysis set. Reasons for exclusion may include, but are not limited to:

- Intercurrent events indicative of SARS-CoV-2 infection prior to 2 weeks after vaccination
- A protocol deviation substantially affecting the immunogenicity outcome (i.e., exclusion from the Immunogenicity Analysis Set)

Another sensitive analysis will further exclude subjects who have significant fold increase in nucleocapsid protein antibody results although neither have positive PCR nor SARS-CoV-2 infection reported as an adverse event.

#### 4.2.3.1. Sensitivity using Multiple Imputation for the Safety Analysis Set

Because the window between vaccination and the primary endpoint measurement is short, the number of subjects with missing data due to intercurrent events or protocol deviations substantially affecting the immunogenicity results is expected to be small. If >5% of data are missing despite the short window, missing values will be imputed via the multiple imputation (MI) method as a sensitivity analysis using the Safety Analysis Set. Missing values will be assumed to be missing at random, such that the reason for the missing value is not dependent on the result itself. As the MI procedure will be performed on the Safety Analysis Set, regardless of protocol deviations, neutralizing antibody results after vaccination that are out of window will be included rather than imputing a “missing” value for full accounting of the available data. Inclusion of serum samples collected out of window will follow the method used for the Sensitivity Analysis using the Safety Analysis Set.

The MI sensitivity analyses will be performed separately for each Part A cohort due to the different background characteristics.

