12.2 Sample Size Calculation

12.2.1 Part A

The primary and key secondary analyses will be tested in the randomized, double-blind component of the trial (Part A) in both Cohort 1 and Cohort 2. Two non-inferiority tests will be performed. Therefore, the sample size calculation is based on a one-sided, 0.0125 type I error, α ,

ABNCoV2-03

to control for both tests. This will maintain the trial-wide α at 0.025 for the one-sided null inferiority hypotheses.

Based on data from the ABNCoV2 phase 2 trial, we assume the common standard deviation to be 0.52 for log_{10} transformed neutralizing antibody titers in both the ABNCoV2 and Comirnaty arms. The test of non-inferiority of ABNCoV2 compared with Comirnaty will be performed by comparing the lower end of the 97.5% CI with a non-inferiority margin of 0.67 in the ratio of neutralizing antibody GMTs between the two groups. We further assume a 10% non-evaluable rate due to dropouts or invalid samples. With an evaluable sample size of 450, a one-sided test with an α of 0.0125 will have approximately 90% power to reject the null hypothesis that ABNCoV2 is inferior to Comirnaty.

A minimum sample size of 400 evaluable subjects will be required for the non-inferiority hypothesis test to be performed for the primary endpoint within each cohort. In the event the evaluable sample size is as low as 400, the power to reject the null hypothesis that ABNCoV2 is inferior to Comirnaty is approximately 86%. In the event that the minimum sample size is not met in one of the cohorts regardless of recruitment effort, data from the cohort will be summarized descriptively and will be integrated in the combined-cohort analyses.

For the key secondary analyses, the number of hypothesis tests to be performed will depend on the number of VOCs of interest circulating at the time of the trial. VOCs will only be formally tested sequentially in the separate Part A cohorts and in the 2 cohorts combined. Discussion of the gatekeeping procedures with regards to the multiple hypothesis tests for the key secondary endpoints is in Section 12.3.

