12.6.3 Sensitivity and Supportive Analyses

The primary analysis will be supported by descriptive summaries (GMT, their 95% CIs and the median) for each time point (pre- and post-vaccination). Besides summarizing data by cohort, summaries and the 95% CI will also be presented for combined Part A Cohorts 1 and 2.

The proportion of subjects with \geq 2-fold and \geq 4-fold increase in neutralizing antibody titers to the SARS-CoV-2 index virus from baseline to 2 weeks after trial vaccination will be summarized using frequencies and percentages within cohort and arm.

ABNCoV2		Clinical Trial Protocol
ABNCoV2-03	Edition 8.0	

Nucleocapsid protein test results will be used to perform additional sensitivity analyses of the primary endpoint. Test results that are indicative of SARS-CoV-2 infection will be used to exclude subjects from the analysis population as potential additional subjects experiencing the intercurrent event of COVID-19 infection prior to the 2 week timepoint.

Since the window between vaccination and the primary endpoint measurement is short, the number of subjects with missing data is expected to be small. If there are any, missing data will be imputed using a multiple imputation method as a sensitivity analysis for subjects who meet the Safety Analysis Set definition.

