## 1. INTRODUCTION

This Statistical Analysis Plan (SAP) details the statistical methodology to be used in analyzing trial data and outlines the key statistical programming specifications. It describes the variables and populations, anticipated data transformations and manipulations, and other details of the analyses not provided in the trial protocol. The SAP is written based on recommendations from *ICH E3: Structure and Content of Clinical Study Reports* and *ICH E9: Statistical Principles for Clinical Trials*. Table, figure, and listing specifications are contained in a separate document.

Deviations from the current protocol are described in Section 4.8. If any unforeseen additional analyses are included in the clinical study report (CSR), they will be clearly described as additional, unplanned analyses in Section 4.8 if added prior to database lock or in the equivalent section of the CSR if ad-hoc analyses are requested post-database lock.

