#### 4.2.6. Supportive Analyses of the Primary Endpoint

The primary analysis will be supported by descriptive summaries (GMT, 95% CI, and median) for each time point (pre- and post-vaccination). Descriptive summaries will be presented for Part A Cohorts 1 and 2 separately and combined.

The proportion of subjects with  $\geq 2$ -fold and  $\geq 4$ -fold increase in neutralizing antibody results to the SARS-CoV-2 index virus from baseline to 2 weeks post-trial vaccination will be summarized using frequencies and percentages along with exact Clopper-Pearson 95% CIs within vaccination arm in each cohort. In addition, a similar summary table as a sensitivity analysis using the Safety Analysis Set will also be presented. Subjects missing a value for a time point who did not achieve a response at a previous time point are counted as non-responders for this sensitivity analysis.

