## APPENDIX 2. SAS CODE FOR MULTIPLE IMPUATION SENSITIVITY ANALYSIS

If >5% of Week 2 neutralizing antibody results are missing for Part A, the multiple imputation code will be run separately for both Part A cohorts, with the appropriate values for prior regimen, shown below, included in each model.

At the time of finalization of the statistical analysis plan, enrollment has completed, and Cohort 1 of Part A did not reach the required sample size for the primary analysis. The MI analysis of Cohort 2 of Part A only will be performed if there are >5% of Week 2 neutralizing antibody results missing.

titersl: the dataset containing the log10 neutralizing antibody results data along with the covariates used in the analysis, one record per subject.

- sex: Male vs. Female
- racegroup: White vs. Other
- agegroup: <65 years vs. ≥65 years
- priorreg (categories different by cohort):
  - Cohort 1:
    - 2 doses of mRNA vaccine,
    - 1 dose or 2 doses of adenovirus-based vaccine,
    - 1 dose of adenovirus-based vaccine followed within 3 months by 1 dose of mRNA vaccine,
    - Other authorized primary vaccination regimen.
  - Cohort 2:
    - 2 doses of mRNA primary vaccines plus 1 booster dose of mRNA vaccine,
    - 1 dose or 2 doses of adenovirus-based primary vaccines plus 1 booster dose of mRNA vaccine,
    - Other authorized primary vaccination and boost vaccination combinations.
- ltiterBL: Log10 Baseline Neutralizing Antibody Result
- ltiterW1: Log10 Week 1 Neutralizing Antibody Result
- ltiterW2: Log10 Week 2 Neutralizing Antibody Result

```
proc mi data=titersl out=titermi nimpute=100 seed=19201
        minimum=[log10(LLOD/2)];
class sex racegroup agegroup priorreg;
var sex racegroup agegroup priorreg ltiterBL ltiterW1;
```

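### The SAP runs the multiple-imputation check only above 5% missing Week 2 data, whereas the protocol requires it for any, and SAP 4.8 does not declare the change

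*SAP*

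**What the plan says.** Protocol 12.6.3 expects few missing values because the interval from vaccination to Visit 3 is short. It then commits itself without a threshold: "If there are any, missing data will be imputed using a multiple imputation method as a sensitivity analysis", for subjects in the Safety Analysis Set.

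SAP 4.2.3.1 shares that expectation but makes the analysis conditional: "If >5% of data are missing despite the short window, missing values will be imputed via the multiple imputation". Appendix 2 gives the condition twice, first as "If >5% of Week 2 neutralizing antibody results are missing for Part A, the multiple imputation code will be run separately" and then, because Cohort 1 under-enrolled, as "The MI analysis of Cohort 2 of Part A only will be performed if there are >5% of Week 2 neutralizing antibody results missing".

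The SAP introduction says "Deviations from the current protocol are described in Section 4.8". Section 4.8 covers the use of nucleocapsid testing, the two kinetics analysis sets, and added analyses of time to infection, thrombocytopenia and hyperkalemia. It does not mention an imputation threshold.

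**The concern.** The primary GMT ratio comes from a model fitted to the Immunogenicity Analysis Set with age and baseline titer as covariates and no imputation (SAP 4.2.2). A vaccinated subject with no Week 2 titer contributes nothing to it. The imputation is the planned check on that omission, and the SAP switches it off at or below 5% missing without saying that it has changed the protocol.

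The trigger is a pooled percentage. A ratio is biased by differences between arms, either in how many results are missing or in how far the missing titers differ from the observed ones. A pooled rate shows neither.

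**Working it through.** **1. Do the texts really conflict?** Both are current. The SAP is version 1.0 of 19 May 2023, written against protocol Edition 7. Edition 8.0 followed on 30 June 2023 and amended Section 12.6.3 itself by adding the nucleocapsid sensitivity analysis. Its change table does not touch the imputation sentence, and the present text still applies to any missing data. Nothing reconciles the two.

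**2. Does another planned analysis fill the gap?**
- SAP 4.2.3, Safety Analysis Set: "All results excluded from the primary estimand analysis will be included with the sensitivity analysis". This restores results that exist and cannot supply one that was never obtained.
- SAP 4.2.3, nucleocapsid analysis: removes further subjects.
- SAP 4.2.6: "Subjects missing a value for a time point who did not achieve a response at a previous time point are counted as non-responders". This is a missing-data rule, but for the 2-fold and 4-fold proportions.
- SAP 4.2.4: no supplementary analyses.

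So at 5% or less missing, no planned analysis examines the GMT ratio for absent Week 2 titers.

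**3. The plan's own figures.** Inputs from Protocol 12.2.1: SD 0.52 log10, margin 0.67, evaluable N of 450 or 400, and "the sample size calculation is based on a one-sided, 0.0125 type I error". Allocation is 1:1 (Protocol 12.1). A true ratio of 1 is my assumption, since the documents do not state one.
- Margin = −log10(0.67) = 0.1739; z = 2.241.
- SE = 0.52 × √(4/N): 0.0490 at 450 and 0.0520 at 400.
- Power = Φ(0.1739/SE − 2.241): 90.4% at 450 and 86.5% at 400, against the stated 90% and 86%. Both reproduce.

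**4. How much can be missing below the trigger?** With the target of 500 per cohort, 0.05 × 500 = 25 subjects. With 475 left, SE = 0.0477, the 97.5% CI half-width is 2.241 × 0.0477 = 0.107, and success needs an observed ratio of at least 10^(−0.1739 + 0.107) = 0.857.

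**5. How far could 25 missing results move the ratio?** Assume that missing ABNCoV2 titers average 0.1 to 0.52 log10 below observed ones and that missing Comirnaty titers do not differ. Shift = (missing on ABNCoV2 / 250) × deficit.

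| Missing on ABNCoV2 | Shift (log10) | Ratio multiplied by | Lower limit of 0.67 becomes |
|---|---|---|---|
| 12.5 (equal split) | 0.005 to 0.026 | 0.989 to 0.942 | 0.662 to 0.631 |
| 25 (all) | 0.010 to 0.052 | 0.977 to 0.887 | 0.655 to 0.594 |

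**6. The same bias as type I error (illustrative only).** Assume that missing titers are lower by d = 0.5 to 1 SD in both arms, with 5% missing overall and 225 per arm. Bias = (share missing on ABNCoV2 − share on Comirnaty) × d × 0.52; type I error at the margin = 1 − Φ(2.241 − bias/0.0490).

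| Split (ABNCoV2 / Comirnaty) | Bias (log10) | Share of margin | Type I error |
|---|---|---|---|
| 5% / 5% | 0 | 0% | 1.25% |
| 7% / 3% | 0.010 to 0.021 | 6 to 12% | 2.1 to 3.5% |
| 8% / 2% | 0.016 to 0.031 | 9 to 18% | 2.7 to 5.4% |
| 10% / 0% | 0.026 to 0.052 | 15 to 30% | 4.4 to 11.9% |

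**7. Would the planned code test the ratio if it ran?** No.
- Vaccination arm is absent from the predictors in SAP 4.2.3.1 and from the VAR and FCS statements in Appendix 2.
- ltiterW2 is named in the FCS regression but not in the VAR list.
- PROC MEANS and PROC MIANALYZE pool one overall mean, with limits labelled 95%. There is no arm difference, GMT ratio or 97.5% CI.

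Adding an arm comparison after an arm-free imputation would not be enough, because it pulls missing values toward the pooled mean. At a true ratio of 0.67 that moves the estimate toward 1 by up to (sum of the two arms' missing shares) × 0.1739/2 = 0.10 × 0.087 = 0.0087 log10, if baseline and Week 1 titers carry no information on arm. That direction favours non-inferiority.

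**The case against.** The undeclared discrepancy cannot be disputed, but its weight can.

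- **The trigger may be met anyway.** The plan assumes 10% non-evaluable from dropouts or invalid samples, twice the threshold. This stands as a reason to expect the imputation to run, but it does not justify dropping it below 5%.
- **There is another missing-data check.** The responder analysis in SAP 4.2.6 has no threshold and uses the same Week 2 titer. A reader might infer that the plan has no missing-data check at all; that goes too far. The gap concerns the GMT ratio, which carries the success criterion.
- **Arm counts are partly visible.** Immunogenicity summaries give n by time point and arm, and SAP 4.6.2 tabulates reasons for exclusion from the Immunogenicity Analysis Set. This stands, although neither is a test of the ratio.
- **The denominator is not badly unclear.** Appendix 2's second statement updates the first, and SAP 4.2.3.1 agrees that only Cohort 2 will be imputed. I place no weight on the wording difference.
- **The error rates are not what imputation would prevent.** A reader might infer that the threshold inflates type I error to as much as 11.9%. The documents do not support that. The figure needs all the loss in one arm and a full SD deficit, and no evidence is given for either. The formula ignores the primary model's adjustment for age and baseline. SAP 4.2.3.1 assumes data are missing at random, so any deficit not predicted by its covariates would remain after imputation.

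**Conclusion.** The point holds as an undeclared conflict between two current texts, with a limited consequence. At 5% or less missing, up to 25 of 500 subjects can lack a Week 2 titer with no planned check of the primary GMT ratio, although the protocol promises one. Under the stated assumptions the ratio moves by about 1% to 11%. It does not move if the arms lose equal shares with equal deficits, and the result is at risk mainly when the lower limit lies near 0.67. The type I error figures only illustrate sensitivity and do not forecast this trial's error rate.

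Sample size, alpha and power are unaffected. The change is worth making because it restores a check the protocol already commits to, but removing the threshold alone would run code that does not estimate the ratio.

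**What to change.** 1. Delete the 5% condition in SAP 4.2.3.1 and in both places in Appendix 2. State that the imputation will be run for Part A Cohort 2 whenever any Safety Analysis Set subject lacks a Week 2 index-virus result.
2. Put vaccination arm in the imputation model, or impute within arm, and add ltiterW2 to the VAR list.
3. Fit the primary model (arm, age, baseline titer) in each imputed data set, pool the log10 arm difference, and report the GMT ratio with its 97.5% CI.
4. Show the number and percentage with missing Week 2 results by arm beside it.

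If the sponsor keeps a threshold, the weaker course is to record and justify it, with its denominator, in SAP 4.8. That removes the contradiction but leaves the gap.

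The cost is SAP wording plus a modest rewrite of the sample code, with no new data. The small downside is that with few, balanced missing results the analysis will closely match the primary one.
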